C.1.b.2. Patient Participant Exclusion Criteria:

Any of the following is regarded as a criterion for exclusion from the study:

1. Any cognitive impairment that precludes informed consent.
2. Patients who, in the opinion of the Principal Investigator, pose an imminent risk of suicide or danger to self or others.
3. Likelihood of potential incarceration such as a conviction or pending charges that may potentially result in imprisonment.
4. Previous enrollment or randomization of treatment in the present study within the 12 months.
5. Behaviors that may cause disruption to a mindfulness group.
6. Patients with symptoms of psychosis, thought disorder, and/or severe mental illness, including schizophrenia, schizoaffective, bipolar disorder, or a current severe episode of major depressive disorder.
7. Refusal of insurance to cover group psychotherapy treatment may lead to exclusion from participation in groups.
8. Patients in their third trimester of pregnancy who foresee conflicts that preclude their commitment to completing all activities.
9. Patients with highly unstable medical problems that put them at a high risk of hospitalization.
10. Temporal Exclusion: Patients with limited English Proficiency as defined by less than 4 out of 7 correct on REALM-SF health literacy screening assessment (equivalent to 7th grade reading level or above) [Note: Patient with limited English Proficiency will be placed on a wait list for specific clinical pilot groups designed for this population, which will be developed for 2016].

C.1.c. Patient Participant fMRI Pilot:

All of the above criteria for patient participants apply to the subset who will take part in the fMRI experiment. In addition, the following criteria will apply:

C.1.c.1. Patient Participant fMRI Pilot additional Inclusion Criteria:

1. Adults 21-60 years old enrolled for participation in the MINDFUL-PC study. (Assessed before the phone-screening using the main study database.)
2. During baseline visit, patient has a history of either major depressive disorder, dysthymia, or generalized anxiety disorder, OR has current mild to moderate symptoms of depression (score range of 10-20 on DASS-21 Depression subscale) or anxiety (score >7 on DASS-21 anxiety subscale). (Assessed before the phone-screening using the main study data from the baseline visit.)

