All MTPC groups will be conducted by clinicians with at least a master's degree and successful completion of the MTPC training program (described below in section C.4.) Participant-observers will be CHA primary care staff, CHA mental health clinicians, CHA mental health care partners, or CHA trainees. MTPC groups, MTPC group leaders, and MTPC participant-observers will be supervised by the CMC clinical medical director ([name]), and the intervention fidelity will be reviewed by the principal investigator ([name]) and expert MBSR teacher trainers, [name] and [name]. Group Leaders will be invited to participate in weekly group supervision by web conferencing with [name] and [name] while they are leading groups. MTPC sessions will be audio-recorded in order to rate fidelity (measured as competence and adherence) to the manual, as well as to provide feedback to MTPC Group Leaders to prevent therapist drift. At the end of each MTPC session, group leaders will fill out a survey of content covered in each MTPC session, rating each other for coverage of content. Group Leaders will review these surveys during supervision. A treatment satisfaction survey will be given at the end of group session #8 to assess for patient impressions of the treatment experience and the group leader's qualities, and these will be reviewed by the Research Coordinator and project manager after the end of each group. If a group leader has below average scores, then the principal investigator will be notified in order to take appropriate corrective measures.

C.3.h. Participant Withdrawal/Termination Criteria:

Withdrawal/Termination criteria for Patient Participants:

Participants may be discontinued from study treatment and assessments at any time. Specific reasons for discontinuing a patient participant from this study are:

1. Voluntary discontinuation by the participant who is at any time free to discontinue his or her participation in the study, without prejudice to further treatment
2. Safety reasons as judged by the investigator
3. Severe non-compliance to protocol as judged by the investigator
4. Incorrect enrollment (i.e., the participant does not meet the required inclusion/exclusion criteria) of the participant
5. Participant lost to follow-up
6. Revealing private information about the study
7. Active substance use disorder or intoxication during study procedures
8. English proficiency below a 7th grade reading level

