Withdrawal/Termination criteria for PCP Participants:

Participants may be discontinued from study treatment and assessments at any time. Specific reasons for discontinuing a PCP participant from this study are:

1. Voluntary discontinuation by the participant who is at any time free to discontinue his or her participation in the study, without effect on the relationship with CHA
2. Safety reasons as judged by the investigator
3. Severe non-compliance to protocol as judged by the investigator
4. Incorrect enrollment (i.e., the participant does not meet the required inclusion/exclusion criteria) of the participant
5. Participant lost to follow-up
6. Revealing private information about the study
7. Active substance use disorder or intoxication during study procedures
8. PCP withdraws from practice at a CHA PCMH

Participants who discontinue will be asked about the reason(s) for their discontinuation and the presence of any adverse events. If possible, they will be seen and assessed by the Principal Investigator. Serious and Unexpected Adverse events will be followed up.

If participants enrolled in MTPC groups are terminated from group treatment for any reason (except incorrect enrollment or safety concerns that endanger the study team), then they will still be expected to complete their outcome assessments, unless the participant revokes informed consent.

C.4. Implementation plan:

C.4.a. MTPC Group Leader Training (See Figure 2 below):

As explained above, this study with 2 x 2 factorial design involves both PCPs and patients as study participants. In addition, CHA behavioral health specialists will receive training during the course of this study to become MTPC group leaders who will provide MTPC groups for patient participants. PCMH behavioral health specialists will concurrently attend the 2.5-hr MBSR group with PCPs (Group 1a), and will also attend an additional 30-60 minute long educational practicum each week. After the conclusion of the 8-week MBSR course, behavioral health specialists will receive an additional 32 hours of training over two weekends to become staff MTPC group leaders. For the first year following their certification, these MTPC group leaders will receive weekly group supervision led by senior mindfulness teachers with supervision from the medical director of the Center for Mindfulness and Compassion who is a board-certified psychiatrist.

Figure 2. Timeline for proposed training activities for PCP participants

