Using an intent-to-treat analysis, we will use logistic regression and Mixed Effects Modeling to evaluate for main effects of MTPC, mindfulness-trained PCPS, and the interaction of the two on binary and continuous ratings of level of action plan initiation and maintenance. We will conduct exploratory linear regression models of post-study mindfulness and self-compassion and overall practice dose as independent variables with level of action plan initiation and maintenance as dependent variables.

The experimental fMRI pilot analyses methods are described below.

6. *Self-Regulation Mechanisms Hypotheses*: In 4 different fMRI tasks, we hypothesize (a) greater activation of ACC and OFC and decreased activation in the amygdala/hippocampus after MTPC intervention compared to before intervention (i.e. a pre/post increase) in an emotional Go/NoGo inhibitory control task, as in Perez 2016 [69], using validated emotional pictures (International Affective Pictures System, IAPS, [70]). The task includes 448 IAPS pictures (50% neutral and 50% unpleasant), which will

be presented briefly (1.5 seconds), while participants either react (Go) or withhold a button press reaction (NoGo), depending on abstract symbols presented on top of the pictures; (b) greater activation of mid-posterior insula after (compared to before) MTPC in a self-compassion task (that contrasts a self-reassurance condition with a self-criticism condition), as in Longe 2010 [71]; (c) greater insula activation during an interoceptive attention task (that contrasts an interoceptive attention condition with an exteroceptive attention condition) as in Farb 2013[72], and d) increases in the rostral ACC (rACC) and ventromedial prefrontal cortex (vmPFC) during the **anticipation of pain** after compared to before MTPC and increased activation in the lateral prefrontal cortex (LPFC) and somatosensory areas **during pain** after compared to before the MTPC, as in Kim 2013 [73]. We hypothesize that all inhibitory control and interoceptive targets will be associated with higher levels of initiation of regimen adherence, while self-compassion, emotion/pain regulation, and interoceptive targets will be associated with higher levels of regimen maintenance.

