Using an intent-to-treat analysis with 290 patients receiving mindfulness training and 144 patients with orientation only, there will be an 80% chance of detecting a significant difference at a two-sided 0.05 significance level. This assumes that the rate of action plan initiation is 0.54 in orientation only (based on Guck et. al. [70]) and the rate of action plan initiation among patients who receive mindfulness training is 0.68 (based on rates of initiation and maintenance of meditation practice in previous pilot MBIs [94]). After the first twenty participants complete the program, an interim analysis of these pilot data may be used to refine the sample size calculation for RCT.

D. Human Subjects Procedures and Confidentiality

D.1. Confidentiality:

D.1.a. Protection of Subject Privacy:

All of the materials collected are for research purposes only, and data will be kept in strict confidence. No information will be given to anyone without permission from the subject. Confidentiality will be ensured by use of identification codes. All data will be identified with a unique numeric identification code and an acrostic that are unique to the subject. Any data collected before a participant discontinues the study is available for use in this research project.

All research session data will be collected using standardized electronic forms on designed using the REDCap database hosted by Cambridge Health Alliance. REDCap (Research Electronic Data Capture) is a secure, web-based application designed to support data capture for research studies, providing an intuitive interface for validated data entry and export procedures to common statistical packages. All data management will be conducted by the research team operating

from CHA. All data collection will take place under the supervision of the [name] and the Data Manager. Data will only be collected by members of the research team.

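### C.3.h lets investigators end outcome assessment for randomised patients and restores it only for those terminated from MTPC groups, which undermines the planned intent-to-treat analysis

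*Combined protocol and SAP*

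**What the plan says.** The patient part of C.3.h opens with a general permission: "Participants may be discontinued from study treatment and assessments at any time". It then lists eight reasons. Voluntary withdrawal and loss to follow-up cannot be avoided. The other six rest with the investigator or study staff: safety, severe non-compliance, incorrect enrolment, revealing private information, substance use disorder or intoxication during procedures, and English reading level below 7th grade. The permission and the list apply to both arms.

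The last paragraph of C.3.h pulls back from this for one group. Patients enrolled in MTPC groups who are terminated from group treatment stay in follow-up whatever the reason, apart from two exceptions and revoked consent: "except incorrect enrollment or safety concerns that endanger the study team), then they will still be expected to complete their outcome assessments".

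On the analysis, C.5.b item 5 says: "Using an intent-to-treat analysis, we will use logistic regression and Mixed Effects Modeling". The sample-size text in C.5.c, repeated in D.4.c, reads: "Using an intent-to-treat analysis with 290 patients receiving mindfulness training and 144 patients with orientation only". D.1.a keeps data collected before discontinuation. No section defines the intent-to-treat set, says how removed patients enter it, gives a rule for missing outcomes or allows for dropout.

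**The concern.** An intent-to-treat comparison needs outcomes on patients as randomised. C.3.h allows outcome collection to stop because of an investigator's decision made after randomisation, in an unblinded trial, and some of the reasons (non-compliance, substance use) could well be related to whether a patient initiates an action plan. Protection is also unequal. A control removed for non-compliance has no continued-assessment clause, while an MTPC patient terminated from the group for the same reason does.

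The gap bites hardest on action plan initiation, the endpoint used to size the trial. In C.3.d.2 and Appendix A Table 3, the APIS-5 is first collected at the post-treatment session around week 8, then at weeks 9, 10, 16 and 24-26. It has no baseline value. A patient taken out of assessments before week 8 therefore has no action plan outcome, and the logistic model drops that patient unless an imputation rule exists.

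**Working it through.** **Inputs.** From C.5.c: 290 MTPC and 144 control patients; "This assumes that the rate of action plan initiation is 0.54 in orientation only"; "the rate of action plan initiation among patients who receive mindfulness training is 0.68"; and "there will be an 80% chance of detecting a significant difference at a two-sided 0.05 significance level". The removal shares (5%, 10%, 20%) are assumptions, because the documents give none.

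**1. Reproduce the stated power.** The normal approximation for two proportions gives power = Φ[(d − 1.96·s0)/s1], where s0 is the pooled standard error and s1 the unpooled one.
- d = 0.68 − 0.54 = 0.14
- pooled rate = (144×0.54 + 290×0.68)/434 = 0.6335
- s0 = √[0.6335×0.3665×(1/144 + 1/290)] = 0.0491
- s1 = √[0.54×0.46/144 + 0.68×0.32/290] = 0.0498
- power = Φ[(0.14 − 1.96×0.0491)/0.0498] = Φ(0.879) = 81.0%

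The stated 80% reproduces, but only with all 434 patients contributing an outcome.

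**2. Removal unrelated to outcome, same share in both arms.** Scaling both arms by (1 − f) gives 79.0% power at f = 5%, 76.9% at 10% and 72.0% at 20%.

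**3. Removal related to outcome.** The assumed extreme is that every removed patient is a non-initiator and drops out of the analysis. The observed rate in the affected arm becomes p/(1 − f).

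(a) *Controls only, planned effect true.*
- f = 5%: control rate 0.54/0.95 = 0.568; difference 0.68 − 0.568 = 0.112; control n 136.8; power Φ[(0.1116 − 1.96×0.0497)/0.0504] = Φ(0.283) = 61%.
- f = 10%: control rate 0.54/0.90 = 0.600; difference 0.080; power about 36%.

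(b) *MTPC only, no true effect (0.54 in both arms).*
- f = 5%: MTPC rate 0.568; spurious difference 0.028; MTPC n 275.5; s0 = 0.0511 and s1 = 0.0511. Upper tail Φ(−1.40) = 8.1%, lower tail 0.6%, so type I error is about 8.7%.
- f = 10%: spurious difference 0.060; type I error about 21.7%.

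| Assumed loss, all non-initiators | Controls only, true 14 points | MTPC only, no effect |
|---|---|---|
| 0% | 14.0 points, power 81% | 0 points, type I error 5% |
| 5% | 11.2 points, power 61% | +2.8 points, type I error 8.7% |
| 10% | 8.0 points, power 36% | +6.0 points, type I error 21.7% |

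The sign of the bias depends on which arm loses patients.

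**The case against.** **The asymmetry is a matter of wording.** The protective sentence concerns group treatment, which only MTPC patients receive; the opening sentence of C.3.h is permissive; and C.3.d.2 schedules the week-8 and six-month surveys for both arms. This stands as an account of how the gap arose, and it may well be unintended. It does not close it: controls can still be taken out of assessments with no clause to keep them in.

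**The plan does not contradict intent-to-treat.** A reader might infer that removed patients are excluded from the analysis. No section says so, D.1.a keeps their earlier data, and a mixed model can use partial data under a missing-at-random assumption. That stands. The weakness is in data collection: with no APIS-5 before about week 8, an early removal leaves nothing on this endpoint to retain or model.

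**The MTPC rate is not shown to be inflated.** A reader might infer that MTPC loses its non-initiators. C.3.h points the other way for most reasons: MTPC patients terminated from the group for non-compliance, disclosure, substance use or reading level remain in follow-up, and control is the less protected arm. This stands, so no direction is claimed.

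**Insurance refusal and disruptive group behaviour are not removal rules.** A reader might count them as triggers peculiar to MTPC. They are entry criteria in C.1.b.2 and are absent from the C.3.h list. The insurance criterion reads "Refusal of insurance to cover group psychotherapy treatment may lead to exclusion from participation in groups", so it concerns groups rather than assessments, and D.7 leaves coverage problems to case-by-case consideration. Nothing says that such a case would be reclassified as incorrect enrolment.

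**Incorrect enrolment is a fact fixed at baseline, and screening is layered** (chart review, phone screen, clinician screen, investigator review). Such removals may therefore be few. Discovery still happens after randomisation and could differ between a clinician-led weekly group and a waitlist, so the exemption is not harmless by construction.

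**Conclusion.** The point holds as a defect in follow-up rules. As written, C.3.h permits investigator-initiated removal from assessments in both arms, protects follow-up only after termination from an MTPC group, and exempts incorrect enrolment and staff-safety cases. Its opening and closing paragraphs also need reconciling on whether removal ends assessment. Together with intent-to-treat power that has about one percentage point of slack (81.0% against 80%) and no missing-data rule, this undermines the planned analysis.

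The size is conditional. At 5% removal, all non-initiators, the result is either a planned difference cut from 14 to about 11 points (power about 61%) or type I error of about 8.7%, depending on the arm affected. Both the share and the all-non-initiator pattern are assumptions chosen to show the extreme; real removals may be rarer and less selective. The documents support neither a direction of bias nor a claim that patients are dropped from the analysis set.

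**What to change.** Amend C.3.h to say that discontinuation for any investigator-initiated reason, in either arm and including incorrect enrolment, ends study treatment only. Outcome surveys then continue by REDCap, paper or phone, remotely where there is a staff-safety concern, unless the patient revokes consent. In C.5.b, define the intent-to-treat set as all randomised patients analysed as randomised, and state how missing action plan outcomes are handled, with a sensitivity analysis that does not assume missing at random.

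No rule on when treatment stops needs to change. No new reading-level check is needed either: C.3.d.2 already applies REALM-SF before randomisation to those scoring below 90% on the consent assessment.

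The cost is one paragraph of protocol text, a short addition to the analysis section and a few more survey contacts. Surveys can already be completed online or on paper, so no new data-collection system is required.

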The implementation project, developed in collaboration with the CHA Center for Mindfulness and Compassion (CMC), will encourage CHA PCPs from across all CHA health care centers to participate in a mindfulness training program. All PCPs will be invited to participate in the study procedures, and those who enroll in the study will naturalistically be assigned to two different groups: those who engage in the mindfulness training program (Group 1) and those who decline to engage in the training program but are still willing to complete study procedures (Groups 2 and 3). The mindfulness training program includes an 8-week MBSR training course of 2.5 hours weekly with an 7-hour day of silent practice at the beginning of week 7 (Group 1a), or an abbreviated 18-hour weekend-long Mindfulness training course (Group 1b). Members of Group 1a will first receive MBSR training from senior MBSR teachers and Group 1b will receive training from CMC faculty and staff. After this MBSR training, members of Group 1a and Group 1b will be able to participate in a once-monthly 2.5 hour-long Mindful Communication course for 10 months during Year 1 of the study. We expect that this Mindful Communication training will eliminate between-group differences from MBSR course models, allowing us to collapse Groups 1a & 1b for research analysis. Both Group 1 and Group 2 will be invited to participate in several survey sessions: prior to starting the mindfulness training implementation project, between PCP study weeks 10 and 14, and then again after PCP study month 12 (see Figure 1a). Group 3 PCPs, enrolled after October, 2016, will not receive mindfulness training, and will only be required to participate in the initial survey session at baseline.

Figure 1a. Study flow schema for PCP participants:

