These tasks will all be conducted in a quiet, closed, and gently lit room located at the Center for Mindfulness & Compassion ([name]). Participants will sit on a chair with their feet flat on the floor, forearms on the table, and with the computer screen in front of them. The research staff member will explain each task to the participant before conducting the trial, and will provide a one-minute break between each task.

C.3.f.8. Provider Resilience Battery for PCP Participants:

The **Maslach Burnout Inventory (MBI)** [61] is the primary scale for assessing burnout. This study will use the original measure, MBI-Human Services Survey, a 22-item scale created for professionals in the human services. This scale examines the perspective with which professionals view their occupation and the people they work with. Items are rated on a 7-point Likert scale from 0 (*never*) to 6 (*every day*). An example item is: “I worry that this job is hardening me emotionally.” The survey contains subscales for examining the factors of emotional exhaustion, depersonalization, and personal accomplishment. Scores are summed for each subscale, and indicate high, moderate, or low levels of the subscale factor (for example, high emotional exhaustion). Scores are usually reported as an average rating for each subscale, rather than a total score. Duration: 4 min.

The 31-item **Workplace Wellbeing Scale (WWS)** [62] measures workplace satisfaction and can be used to compare data across various categories such as gender and occupational level. Items on this scale are evaluated as four subscales: work satisfaction, organizational respect for the employee, employer care, and intrusion of work into private life. Summed items for each subscale generate a numerical score that corresponds to low, medium, or high levels of each subscale (for example, low employer care is indicated by a score between 0-7 for the employer care subscale). The WWS includes questions such as “Does your work eat into your private life?” Each item is scored on a 5-point Likert scale from 0 (*Not at all*) to 4 (*Extremely*). Positive questions are reverse scored. Duration: 4 min.

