Mixed Effects Modeling to evaluate for main effects of PCP mindfulness training and main effects of Patient training level (1 hour vs. 8 week) for each survey, as well as the interaction effect with relevant covariates.

3. *Health Outcomes Hypotheses*: We hypothesize reductions in depression, anxiety and stress as a main effect of MTPC. Finally, we hypothesize reductions in use of medications prescribed for symptom reduction (benzodiazepines, opioids, etc.), overall improvement in markers of health maintenance and chronic illness management (i.e. PQRS data). We hypothesize the highest levels of initiation and maintenance of self-management action plans among MTPC group with Mindfulness-trained providers.

Mixed Effects Modeling to evaluate for main effects of PCP mindfulness training, main effects of Patient training level (1 hour vs. 8 week) for each outcome, as well as the interaction effect with relevant covariates.

4. *Provider Resilience Hypothesis*: We hypothesize greater workplace well-being, reduced experience of burnout, and increased resiliency among providers as a main effect of provider MBSR + Mindful Communication training.

We will use Mixed Effects Modeling to evaluate for main effects of PCP mindfulness training and time for each survey and the interaction of the two.

5. *Medical Regimen Adherence Hypotheses*: We hypothesize a main effect of MTPC group status on levels of initiation and maintenance of medical regimen health behavior change, as measured by the APIS-5 self-report score. The highest levels will be demonstrated among the MTPC group participants with mindfulness-trained providers. We hypothesize that total formal mindfulness practice, post-study total mindfulness score, baseline mindful non-judgment score, and self-compassion will be associated with successful initiation and maintenance of action plans. Action plan initiation will be validated by increases in step count, and increases in number of active periods, changes in sleep, changes in mindfulness practice, and changes in nutritional habits.

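### Hypothesis 4 rests on a training main effect among PCPs who chose their own group; the training-by-time term that would remove a stable baseline gap is listed but not made to decide

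*Combined protocol and SAP*

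**What the plan says.** The hypothesis, given in A.2.b and repeated in C.5.b item 4, expects better workplace well-being, less burnout and "increased resiliency among providers as a main effect of provider MBSR + Mindful Communication training". Aim 4 in A.2.a also speaks of main effects. The analysis in item 4 is a mixed model to "evaluate for main effects of PCP mindfulness training and time for each survey and the interaction of the two". Items 2 and 3 add "as well as the interaction effect with relevant covariates"; item 4 names no covariates.

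On how PCPs reach their group, C.3.a says that "those who enroll in the study will naturalistically be assigned to two different groups": those who take the training (Group 1) and "those who decline to engage in the training program but are still willing to complete study procedures" (Groups 2 and 3). Groups 1 and 2 are surveyed before training, at weeks 10-14 and after month 12. Group 3, enrolled after October 2016, is surveyed at baseline only.

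The Provider Resilience Battery (C.3.f.8) holds the Maslach Burnout Inventory (three subscales), the Workplace Wellbeing Scale (four subscales) and the Jefferson Scale of Empathy. Of the Maslach inventory it says: "Scores are usually reported as an average rating for each subscale, rather than a total score". It is described as the primary scale for burnout, but no subscale is chosen, and no instrument in the battery is a resilience scale. Table 2 marks all three instruments at the pre-study session and at both later sessions. The pre-treatment visit text in C.3.d.1 does not list this battery; it lists an Experience of Caring Battery instead.

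C.2.a sets a target of at least 25-40 PCPs in Group 1 and at least 25-40 in Groups 2 and 3 together. No power or effect size is given for Hypothesis 4.

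**The concern.** PCPs who volunteer for a long mindfulness programme may differ in burnout or well-being from those who decline it, and such a difference would be present before training. A training main effect in a model that includes the pre-training visit does not separate that difference from what training changed; the training-by-time term does.

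Item 4 includes both terms and says of neither that it decides. The hypothesis names the main effect. An analyst who follows that wording could report support for Aim 4 when training did nothing, or miss a real benefit because trainees started out worse. The visit and the score that decide are also left open.

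**Working it through.** There is no stated figure for Hypothesis 4 to reproduce: the power statements in C.5.c and D.4.c for the main trial concern patients' action plan initiation. The calculation below therefore rests on assumptions.

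**Inputs from the documents:** three survey times; 25 or 40 PCPs per group; the group, time and group-by-time terms.

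**Assumed, not in the documents:** SD 1 at each visit; equal correlation r of 0.5 to 0.7 between visits; a stable gap D of 0.3 or 0.5 SD; complete data; two-sided 0.05 (the level the plan states for patients).

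**1. What the main effect estimates.** With gap D at all three visits and a training effect E at the two later ones, the main effect is (D + (D + E) + (D + E))/3 = D + 2E/3. The gap enters whole and the effect enters at two-thirds. The difference in change from baseline is (D + E) − D = E.

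**2. No training effect (E = 0).** For the main effect, SE = sqrt[(2/n)(1 + 2r)/3]. At n = 25 and r = 0.5, SE = sqrt(0.08 × 0.667) = 0.231; for D = 0.3 the ratio is 1.30 and the rejection probability is 25%. The full set:

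| n per group | r | D = 0.3 | D = 0.5 |
|---|---|---|---|
| 25 | 0.5 | 25% | 58% |
| 25 | 0.7 | 22% | 51% |
| 40 | 0.5 | 38% | 78% |
| 40 | 0.7 | 32% | 70% |

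These are normal approximations. Simulated t tests give slightly lower values, from about 22% to about 77%. The test of change from baseline stays at about 5% in every cell.

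**3. True effect, trainees worse at baseline (E = 0.5, D = −0.3, n = 40, r = 0.6).**
- Main effect: −0.3 + 0.333 = 0.033; SE = sqrt(0.05 × 2.2/3) = 0.191; power about 5%.
- Change to the last visit: SE = sqrt[(2/n) × 2(1 − r)] = sqrt(0.05 × 0.8) = 0.20; 0.5/0.20 = 2.5; power about 70%.
- Mean of the two later visits minus baseline: SE = sqrt[(2/n) × 1.5(1 − r)] = sqrt(0.05 × 0.6) = 0.173; power about 82%, or 81% in simulation.

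**4. Baseline-adjusted post score.** With a stable gap this estimate is off by D(1 − r): 0.3 × 0.3 = 0.09 SD up to 0.5 × 0.5 = 0.25 SD. With no training effect it rejects in about 7% to 23% of simulated trials over the settings of step 2. It does not do the same job as change from baseline in self-selected groups.

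**5. Number of scores.** If independent, the chance of at least one false positive is 1 − 0.95^3 = 14% for three instruments, 1 − 0.95^7 = 30% for the seven burnout and well-being subscales, and 1 − 0.95^8 = 34% with empathy added. Correlation between scores lowers these figures.

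**The case against.** The strongest reply is that the needed contrast is already in the plan, since item 4 lists the interaction of training and time. In a protocol built on a 2 × 2 layout, 'main effect' may also simply mean provider training as a factor, as opposed to its combination with patient training. This stands in part: the model does not have to be changed, and the plan cannot be said to have left the right term out. It does not settle which term decides, and the only term the hypothesis names is the main effect.

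A reader might infer that any pre-existing difference would be counted as benefit. The documents do not support that. Only a gap favouring trainees inflates the claim; a gap the other way hides benefit, and one present only at baseline enters at D/3. Nor do the documents show that a gap exists; its size here is a scenario.

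A reader might also infer that eight scores will each be tested as a claim. Eight is a count from the battery. The plan says each survey, and Hypothesis 4 does not name empathy, so the family could be three instruments or seven subscales. The Maslach inventory is singled out for burnout, so the plan is not silent on instruments.

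Finally, the PCP part is openly described as naturalistic and quasi-experimental, which lowers its weight but does not make the main effect the right contrast. Because Group 3 counts towards the 25-40 controls and has no follow-up, the controls with three visits may be fewer than assumed above.

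**Conclusion.** The concern holds for the choice of deciding term. Following Hypothesis 4 as worded gives an answer that mixes baseline differences with training effects: about 22% to 77% rejections with no training effect, against 5% for change from baseline, for stable gaps of 0.3 to 0.5 SD, correlation 0.5 to 0.7, 25 to 40 per group and complete data. In the reverse case of step 3, power falls to about 5% where change from baseline has about 70% to 81%. These sizes depend on the assumed gap and correlation; the direction of the problem does not.

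Two lesser points stand beside it: no deciding visit or score is named, and resiliency has no scale of its own. Training-by-time removes a gap that is constant over time. It does not remove differing trends or regression to the mean, so it would not turn this into a randomised comparison.

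**What to change.** - In A.2.b and C.5.b item 4, replace the main effect by the training-by-time contrast as the deciding test: the difference between groups in change from the pre-study survey to week 56. Do not offer the baseline-adjusted post score as equivalent.
- State that Group 3 does not contribute to this contrast, and leave those PCPs out of the model that estimates it. They have no change score, and a likelihood fit would otherwise use their baseline values in the control group's baseline mean.
- Reconcile the pre-treatment visit text in C.3.d.1 with Table 2 on whether the Provider Resilience Battery was given at baseline. The contrast cannot be computed without those scores.
- State the covariates, or state that there are none.
- List the scores as a family with a multiplicity adjustment such as Holm, or label them exploratory. Choosing a single subscale now would be a preference formed after data collection.
- Tie resiliency to a listed score, or drop it from the claim.

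The cost is a wording change, provided that the baseline battery was collected. Fewer scores can be claimed at 0.05. PCP study visits closed on 10 February 2017, so the change must be dated and described as made after PCP data collection ended, and the result reported as observational.
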